Subjects with moderate levels of ADHD will be enrolled, including individuals on no current treatment and those receiving current pharmacotherapy for ADHD. Six weeks is a typical interval over which stimulant effect on ADHD may be seen, and we will extend observation to 12 weeks to measure L-Threonic acid Magnesium salt effects that might occur during a reasonable time frame for clinical intervention.

II. SPECIFIC AIMS

Aim 1: Assess the safety of the effects of L-Threonic acid Magnesium salt on cognitive functioning when administered to adults with ADHD.

Hypothesis 1: L-Threonic acid Magnesium salt will be well tolerated in adults.

Aim 2: Assess effect of L-Threonic acid Magnesium salt on attention, behavioral control and cognition. Hypothesis 2: Compared to pre-administration baseline, administration L-Threonic acid Magnesium salt will yield a significant reduction of (2a) attention and behavioral ADHD traits (as measured by the AISRS) and 2b) ratings of clinical global improvement, (2c) symptoms of executive dysfunction (as measured by BRIEF-A subscales).

Hypothesis 3: Compared to pre-administration baseline, performance on individual neuropsychological tests will improve (as measured by a) elements of the Cambridge Neuropsychological Test Automated Battery, and b) tests used to estimate IQ, and c) higher correlation between performance on neuropsychological tasks.

We also will explore whether baseline red blood cell magnesium level, deficits on BRIEF or neuropsychological tests predict improvements on AISRS or BRIEF measures.

These supplements are not known to diagnose, cure, mitigate, treat or prevent ADHD.

III. SUBJECT SELECTION

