Subjects who: 1) develop intolerable AE(s) despite dose adjustments; 2) have (a) clinically relevant serious AE(s) as determined by the investigator; 3) have worsening ADHD symptoms (much worse or very much worse as rated on CGI-Improvement at two consecutive visits); or 4) have emergent adverse mental health state including psychosis, suicidality, substance use, or worsening mood and/or anxiety; 5) are non-adherent to study procedures or withdraw from the study; 6) intend to be or become pregnant will no longer continue in the study. If study participation is discontinued due to safety reasons, participants will receive two follow-up visits, giving adequate time for appropriate psychiatric referrals to treaters in their communities.

Subjects found to be taking substances listed as exclusionary during the course of the study may be discontinued based on PI evaluation of their eligibility.

VI. BIOSTATISTICAL ANALYSIS

As this is a single-arm, open study designed to evaluate the effectiveness and safety/tolerability of L-Threonic acid Magnesium salt, formal power analyses are not warranted.

Data processing and management will follow procedures developed by the investigators and used in ongoing studies. 15 subjects will receive L-Threonic acid Magnesium salt. Changes in outcome ratings within and between study groups will be tested. All analyses will be intention to treat (ITT), utilizing.

Our exploratory hypotheses are as follows. Our primary test of Hypothesis 1 will be review of the occurrence of moderate or severe adverse events. Hypothesis 2 will be tested by evaluating whether over the course of L-Threonic acid Magnesium salt administration the following are seen: a) at least a 25% reduction in ADHD as rated by the AISRS total score; b) CGI of much or very much improved, c) reduced symptoms of executive dysfunction (defined by a 0.5 standard deviation improvement on BRIEF-A self-report total or subscale scores). Hypothesis 3 predicts that there will be measurable improvement in cognitive function, as

measured by a) statistically significant improvement on CANTAB tasks, and b) improvement in performance on the WASI matrix, used to estimate IQ, and c) increased correlation between performance on domains of function.

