For ADHD AISRS, BRIEF, and CANTAB evaluations, we will compare pre-treatment and study visit values of measures using paired t-tests, via an intention-to-treat analysis with the last observation carried forward (LOCF) for subjects who did not complete the full study. Alpha will be set at 0.05 for all comparisons.

We will also explore descriptively whether baseline erythrocyte magnesium level, or deficits in BRIEF or CANTAB ratings as measured against norms predict improvement on AISRS or BRIEF ratings.

VII. RISKS AND DISCOMFORTS

All efforts are made to minimize risks to subjects. Consistent with good clinical practice, safety will be monitored by the Principal Investigator, and will reflect the oversight of co-investigator study clinicians. Adverse events will be recorded and reported according to institutional policies. Risks of the study agent have been incorporated into the exclusionary criteria for this proposal.

Study clinician evaluation and subject questionnaires:

Some questions may make subjects feel uncomfortable. Subjects may refuse to answer any question they wish. In the event that a participant reports risk of harm to himself or herself, or to another person, study clinicians will assess the level of risk, and take appropriate actions, including disposition of an immediate referral to a local Psychiatric Emergency Room.

Study Agents –MMF202 (6-hour release) and MMF303 (12-hour release):

The active ingredient in MMF202 (6-hour release) and MMF303 (12-hour release) is L-Threonic acid Magnesium salt, is considered a dietary supplement that the manufacturer has self-certified as fulfilling the US Food and Drug Administration criteria for agents that are Generally Regarded as Safe. There are few risks to taking L-Threonic acid Magnesium salt orally. Magnesium is known to cause gastrointestinal discomfort, nausea, vomiting, or diarrhea. Although occurrences are rare, very large amounts of magnesium might cause hypermagnesemia with symptoms including thirst, hypotension, drowsiness, confusion, loss of tendon reflexes, muscle weakness, respiratory depression, cardiac arrhythmias, coma, cardiac arrest, and death. There have been only two reports of death from hypermagnesemia that we found record of. ⁴³ The dose prescribed to subjects as part of this study will unlikely lead to hypermagnesemia, as extremely high doses of magnesium are required to produce this effect.

ADHD Pharmacotherapies:

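### Exploratory criterion 3c treats a higher correlation between tasks as improved cognition, but a correlation ignores the level of performance, and the plan gives it no threshold, summary or usable test

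*Combined protocol and SAP*

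**What the plan says.** Section VI (Biostatistical Analysis) introduces the hypotheses as exploratory and states: "Hypothesis 3 predicts that there will be measurable improvement in cognitive function". Three measures follow, joined by the word and: (a) "statistically significant improvement on CANTAB tasks"; (b) better performance on the WASI matrix; (c) "increased correlation between performance on domains of function". Section II (Specific Aims, Hypothesis 3) gives the third measure as "higher correlation between performance on neuropsychological tasks", again as a way of showing that test performance improves.

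The only test named in Section VI is in this sentence: "For ADHD AISRS, BRIEF, and CANTAB evaluations, we will compare pre-treatment and study visit values of measures using paired t-tests". It is followed by "Alpha will be set at 0.05 for all comparisons". The sample size is given as "15 subjects will receive L-Threonic acid Magnesium salt".

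For 3c, neither section states which tasks or domains are to be correlated, whether one pair or an average is meant, how large a rise is needed, which visit is used, or what test or interval applies.

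**The concern.** There are two separate problems.

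The first is the construct. A correlation across subjects describes how similarly subjects are ranked and spaced on two tasks. Adding or subtracting a constant from everyone's score leaves it unchanged. It rises when variation shared by the tasks grows relative to task-specific variation, whether that comes from gains or losses. The background section gives no reason why closer correlation should mean better cognition.

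The second is the decision rule. A paired t-test needs one difference per subject, whereas a correlation is one number per visit for the whole group. The alpha sentence therefore has no method to act on for 3c. Part (a) asks for statistical significance; part (c) does not.

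At stake is how a pilot intended to guide a later double-blind study (Section I) reports its cognitive results. A rise in correlation could be reported as cognitive improvement when it is noise or accompanies decline. Conversely, if 3c is a required part, a real gain could be reported as unsupported.

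**Working it through.** The plan gives no power or error-rate figure for 3c, so there is none to reproduce.

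**Inputs from the documents.** n = 15 (Section VI). Eight CANTAB subtests (Section V, Assessments and Instruments), which at one score each give 8 × 7 / 2 = 28 pairs.

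**Assumptions, not in the documents.** One score per subtest; multivariate normal scores; between-task correlation 0.3 (range 0 to 0.6); same-task retest correlation 0.5 to 0.8 (range from 0).

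**1. Chance of a rise with no true change.** The same correlation matrix was simulated at both visits, counting how often the later sample correlation exceeded the earlier one.

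| What must rise | Share of simulated trials |
|---|---|
| One named pair | about 50% (48–51% over the full range) |
| Mean of 28 pairs | about 50% (49–51% over the full range) |
| Any of 28 pairs | over 99% (99–100% over the full range) |
| All 28 pairs | under 0.1% (about 1% or less over the full range) |

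The 50% follows from symmetry: with the same distribution at both visits, either sample correlation is equally likely to be the larger. Carrying 3 of 15 subjects forward from baseline (51%) or using n = 25 (48–49%) changes little.

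**2. Independence from the level of performance.** A uniform fall of 0.5 SD on every task leaves the rate for one pair or the mean at 49–50%. A uniform gain does the same, since a constant shift cancels out of a correlation.

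**3. A rise while performance falls.** Take two tasks with unit variance and covariance 0.30. Let each subject decline by an amount shared by both tasks, mean 0.5 SD and SD 0.8 (variance 0.64). Then

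- later correlation = (0.30 + 0.64) / (1 + 0.64) = 0.94 / 1.64 = 0.57.

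In simulation at n = 15 the sample correlation rose in 82% of trials, and in 69% it rose while both task means fell.

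This is a possibility, not a rule. Doubling the spread of every task leaves the correlation at 0.30. Adding task-specific variation of the same size lowers it: 0.30 / 1.64 = 0.18.

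**4. Precision at n = 15.** By Fisher's z, atanh(0.30) = 0.310 with standard error 1/√12 = 0.289. The 95% limits are 0.310 ± 1.96 × 0.289 = −0.256 to 0.875, or r = −0.25 to 0.70. For a change between visits, treating them as independent (an approximation), the standard error is √(2/12) = 0.408. A pair starting at 0.30 would need to reach tanh(0.310 + 1.96 × 0.408) = tanh(1.110) = 0.80 for two-sided significance.

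**5. Joint reading of (a), (b) and (c).** Take no true change, and let (a) mean any of eight CANTAB tasks significantly better, (b) any numerical rise on the WASI matrix, and (c) a rise in the mean correlation. All three are then met in about 5–6% of simulated trials, although (c) alone is met in about 50%. If performance truly improves by a constant and correlations do not change, step 2 shows that (c) still fails about half the time, however large the gain.

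**The case against.** The strongest defence has four parts.

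- **The parts are joined by and.** Read plainly, 3c cannot carry Hypothesis 3 alone, and decline could not satisfy it because (a) and (b) need better scores. This stands as one reading, but the plan states no joint rule. On that reading the fault changes direction: an uninformative required part blocks a real improvement about half the time when correlations are unchanged.
- **Alpha is 0.05 for all comparisons.** A reader might infer from 3c that any numerical rise, however small, is the stated rule for success. The documents do not go that far, because the alpha sentence could be meant to cover 3c. What stands is narrower: no method is named through which that alpha could apply.
- **The chance rate depends on the reading.** A reader might also infer that the criterion is simply met half the time by chance. The documents do not support that as a general statement. It holds for one pair or one mean correlation. Section VI speaks of domains and does not define them; the grid of 28 pairs is an assumption.
- **The hypotheses are exploratory.** This stands and limits the consequence: no dosing, stopping or sample-size decision is tied to 3c. However, Section VI has a separate place for questions to be explored descriptively, and 3c is instead listed as a measure of improvement.

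It would likewise go too far to say that decline or wider spread raises a correlation. It can, when the added variation is shared across tasks; otherwise the correlation may stay the same or fall.

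**Conclusion.** The concern holds in limited form. Criterion 3c is not a measure of improved cognitive function, because it ignores the level of performance and can rise when performance falls (0.30 to 0.57 in the worked example). It also has no threshold, summary or usable test. The chance of meeting it with no true change is about 50% for one pair or the mean correlation, and runs from under about 1% to over 99% across 28 assumed pairs, depending on a choice the plan leaves open.

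The 50% result barely depends on the assumed correlations; the figures for any or all pairs rest on the assumed set of eight scores, and the worked example rests on its assumed shared decline. The documents do not show that 3c alone would make Hypothesis 3 succeed, because they do not say whether the three parts are required together or count separately. Under either reading 3c adds no information about improvement. The consequence is confined to the reporting of an exploratory hypothesis and to what is carried into the later trial.

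**What to change.** In Section II (Hypothesis 3) and Section VI, stop counting 3c as a measure of improvement and base Hypothesis 3 on change in performance, that is, on 3a and 3b.

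If the question remains of interest, keep it as descriptive only and specify:

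- score directions aligned so that higher means better on every task;
- one summary, the mean inter-task correlation over a named list of tasks;
- the change in that summary from pre-treatment to week 12, with a 95% confidence interval from a bootstrap that resamples subjects and keeps both visits of each subject together;
- a statement that the result does not count as support for Hypothesis 3.

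The cost is two wording changes and, if 3c is kept, a short bootstrap. No new data, visits or participants are needed. The downside is the loss of one favourable-sounding criterion.

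### WASI matrix (3b) and CGI (2b) have no named test or decision rule; read as written, 3b is met in about half of trials with no true change, and 2b's error rate cannot be determined

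*Combined protocol and SAP*

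**What the plan says.** All references are to the combined protocol and SAP.

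- **Section II (Specific Aims)** predicts a significant reduction from the pre-administration baseline. The prediction covers the AISRS, "2b) ratings of clinical global improvement, (2c) symptoms of executive dysfunction (as measured by BRIEF-A subscales").
- **Section VI (Biostatistical Analysis)** turns the hypotheses into criteria. For Hypothesis 2 it states: "Hypothesis 2 will be tested by evaluating whether over the course of L-Threonic acid Magnesium salt administration the following are seen". The second item is "b) CGI of much or very much improved".
- For Hypothesis 3, the first criterion is improvement "measured by a) statistically significant improvement on CANTAB tasks". The second is "b) improvement in performance on the WASI matrix, used to estimate IQ". The third, 3c, is a higher correlation between performance domains.
- The method comes at the end of section VI: "For ADHD AISRS, BRIEF, and CANTAB evaluations, we will compare pre-treatment and study visit values of measures using paired t-tests". The same sentence carries the last observation forward for non-completers. The next says "Alpha will be set at 0.05 for all comparisons".
- **Section V (Subject Visits; Assessments and Instruments) and the visual timeline** schedule CGI at baseline and every later office visit (weeks 3, 6, 9 and 12). WASI-II is taken at screening or baseline and again only at endpoint.

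**The concern.** The method sentence leaves out CGI and WASI, so the criteria in section VI are the only operational statement of what would count as support for 2b and 3b. Those criteria are loose in different ways.

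For 3b the contrast is within one sentence: CANTAB must improve significantly, while the WASI matrix need only improve. For 2b, a favourable CGI rating must be seen during treatment, but the plan does not say in how many subjects, at which visit, or against what expected rate. CGI-Improvement is itself a rating of change and has no pre-dose value. The baseline comparison promised in section II therefore cannot be made by simply adding it to the list of paired t-tests.

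Section I says the pilot is to guide a later double-blind study of the selected outcomes. If 3b is declared met on a chance gain, or 2b on a reading chosen after the ratings are known, an outcome could be carried forward without evidence.

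**Working it through.** **Inputs from the documents.** n = 15 subjects receiving the agent (section VI; section V allows up to 25 to be recruited); alpha 0.05; paired t-test as the named method. Sidedness is not stated, so two-sided is assumed.

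**Inputs not in the documents, assumed and varied.** Retest gain d on the WASI matrix, in SDs of the individual changes; p, the chance that a subject is rated much or very much improved on CGI without any true effect.

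**The plan's own figure.** No power or sample-size figure exists to reproduce. The stated alpha was checked: a two-sided paired t-test with n = 15, simulated 200,000 times under no change, rejects in 4.9% of runs. The named test delivers its 0.05 where it is applied.

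**Criterion 3b, read as mean change above zero.** For normally distributed changes, P(met) = Φ(d × √15), with √15 = 3.873. The paired t-test claims improvement when t exceeds t(0.975, 14) = 2.145, that is, when the mean gain exceeds 2.145 / 3.873 = 0.55 SD. Its rate of claiming improvement comes from the noncentral t distribution.

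| d (no true effect of the agent) | Bare improvement | Paired t-test, improving direction |
|---|---|---|
| 0 | Φ(0) = 50% | 2.5% |
| 0.1 | Φ(0.387) = 65% | 5.5% |
| 0.2 | Φ(0.775) = 78% | 10.8% |
| 0.3 | Φ(1.162) = 88% | 19.0% |
| 0.5 | Φ(1.936) = 97% | 43.8% |

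The 50% in the first row depends neither on n nor on any assumed gain.

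**Criterion 2b, under different readings of the same words (n = 15).**

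- *At least one subject:* 1 − (1 − p)^15 gives 14% at p = 1%, 26% at 2%, 37% at 3%, 54% at 5%, 79% at 10% and 96% at 20%. It reaches 50% at p = 1 − 0.5^(1/15) = 4.5%.
- *At least three subjects* (binomial tail): 3.6% at p = 5%, 18% at 10%, 60% at 20%.
- *A majority, 8 or more:* 0.003% at p = 10%, 0.4% at 20%, 5.0% at 30%.
- *Every subject:* with a true response rate of 80%, the criterion is met in only 0.8^15 = 3.5% of trials.

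The visit matters too. If any of the four post-baseline visits counts, one subject suffices, and ratings are independent with p = 5% per visit, the rate is 1 − 0.95^60 = 95%. The result thus runs from near 0 to near 1 according to choices the plan does not make.

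**The case against.** Four points can be made for the plan.

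1. **Testing is intended.** Section II predicts a significant reduction that covers 2b. Section VI says that changes in outcome ratings will be tested and sets one alpha for all comparisons. This stands, and a reader who inferred that CGI and WASI are to go untested would be going too far. None of these statements names a method, visit or threshold for either measure, however.
2. **A change rating can be tested.** It might be inferred that CGI-Improvement cannot be tested because it lacks a baseline. That is not so: it can be compared with no change, or its responder proportion with a reference rate. The gap is that the plan chooses neither.
3. **Bare improvement is a reading.** The lead-in to Hypothesis 3 speaks of improvement that can be measured, and no text says that any gain above zero suffices. The 50% therefore belongs to the literal reading. That reading is the natural one, since significance is required for 3a and not for 3b.
4. **The hypotheses are exploratory**, in an open-label pilot of tolerability and feasibility. Descriptive reporting of CGI would be quite acceptable. The plan, however, says Hypothesis 2 will be tested.

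The most tempting stronger reading is that 2b, like 3b, is met half the time or more under no effect. That needs one responder to be enough and a no-effect rate of at least 4.5%. The documents state neither, and under a majority reading the rate is 5% or less for p up to 30%.

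**Conclusion.** The concern holds as an incomplete specification, with a known size for 3b only.

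- **3b:** taken literally, met in about 50% of trials with no true change, against 2.5% under the paired test already used for CANTAB. Any retest gain raises this; the 78% figure rests on an assumed 0.2 SD.
- **2b:** no subject count, visit, reference rate or test is given, so no error rate can be attached to it.
- **3c:** likewise has no named test.

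The figures assume 15 analysed subjects, two-sided alpha and normally distributed changes. The point does not affect the AISRS, BRIEF or CANTAB t-tests. It should be corrected because the correction is cheap and the results are meant to inform the next trial.

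**What to change.** 1. **3b.** In section VI, add the WASI-II matrix score to the measures compared by paired t-test, and reword 3b to require statistically significant improvement, as 3a does. State that an uncontrolled paired test does not remove practice effects: with an assumed gain of 0.2 SD it still claims improvement in about 11% of trials. Because WASI-II is repeated only at endpoint, carrying forward an entry value amounts to recording no change, and the text should say so.
2. **2b.** Report the proportion rated much or very much improved on CGI-Improvement at week 12 or the drop visit, with all dosed subjects as denominator, missing ratings counted as non-response, and an exact 95% confidence interval. Call it descriptive unless a justified reference rate is stated, and do not declare it met because isolated responders are seen. The reference rate matters: an exact test with upper tail at most 0.025 needs at least 4 of 15 responders against 5%, 5 against 10%, 7 against 20% and 9 against 30%.
3. **Supportive test, optional.** Paired change in CGI-Severity, using ratings already scheduled at baseline and each office visit.
4. **3c.** Label it descriptive or name a method.

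**Cost.** A few sentences in section VI, with no new visits, subjects or data. Criterion 3b becomes harder to meet: at n = 15 the paired t-test has about 44% power for a true change of 0.5 SD of the differences and 82% for 0.8 SD.

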Preclinical studies suggest that L-Threonic acid Magnesium salt can modulate rat brain function. Slutsky, et al (2010) demonstrated that oral delivery of L-Threonic acid Magnesium salt to rats achieves significantly higher levels than the control feed, whereas magnesium chloride, magnesium orotate, or magnesium gluconate did not. This report also demonstrated increases in synaptic density in hippocampal regions, and reversed task impairment in Alzheimer's-model rodents. Therefore, L-Threonic acid Magnesium salt could be expected to have central nervous system effects in human subjects, including potentially alleviation of ADHD symptoms.²³

The risk profile of magnesium supplementation is favorable relative to that of pharmaceuticals currently available under FDA indication for Attention Deficit Hyperactivity Disorder. In a rat model, magnesium chloride at an intake of up to 2.5% of food resulted in no significant toxic effects. ³⁰ In addition, acute and chronic supplementation for hypomagnesemia has been well tolerated with a favorable safety profile. ^{31, 32}

Magnesium supplements, including L-Threonic acid Magnesium salt, are widely purchased and consumed. The most common side effect of magnesium supplementation may be diarrheic effects. Neurocentria, the makers of the study agent MMFS202 6-hour release and MMFS302 12-hour release, has communicated that in preliminary studies they have not found significant side-effects with 2 g/day of L-Threonic acid Magnesium salt.³³ Some subjects reported sleepiness, but it subsided after a few days. There were also some reports of vivid dreams and restlessness.³⁴

Conventional therapies for ADHD are thought to work in part through reuptake blockade and/or increased release of the catecholamines dopamine and norepinephrine. ¹³ L-Threonic acid Magnesium salt, therefore, offers a novel mechanism of modulating cognitive function. If effective and well tolerated, it could offer a novel modality for support of ADHD or related cognitive deficits.

Because L-Threonic acid Magnesium salt could have positive effects on ADHD symptoms, it has not yet been evaluated in adults with ADHD, and is expected to be well tolerated, we propose to conduct an open-label pilot study enrolling 15 adults with ADHD to receive L-Threonic acid Magnesium salt. The study is designed to evaluate tolerability and feasibility of the protocol, and guide development of future more definitive doubleblind study of the selected outcomes.

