Vital signs (blood pressure, pulse, weight) will be measured at every in-office visit. Height will be measured at baseline and at the end of the study. A urine drug screen will be performed at screening, week 6, and week 12. If the participant is found to have taken an illicit drug, he/she will have a discussion with the doctor to determine if he/she can be in the study. Subjects will be discontinued if there is suspicion of ongoing substance use. For safety purposes, an EKG will be conducted during screening and at the endpoint of the study. Females who are able to have children will also have a urine pregnancy test at screening, week 6, and week 12.

If a participant has a positive pregnancy test she will not be able to take part in the study. Female subjects of childbearing potential must agree to use a medically acceptable form of birth control (such as male for female condoms with or without spermicidal agent, diaphragm or cervical cap with spermicide, medically prescribed IUD, hormonal contraceptives like birth control pills, or abstinence) while they are receiving study agent and for 1 month after the last dose of study agent. In the event that a subject becomes pregnant, we will ask the subject's permission to obtain information about the outcome of the pregnancy and the condition of the newborn. Those subjects who terminate study participation before the completion of the study will be asked to complete all tasks scheduled to take place on the final study visit at the time of study discontinuation.

We will draw blood samples at the screening visit and at study endpoint to determine erythrocyte (red blood cell or RBC) levels of magnesium and calcium. Samples will be analyzed by LabCorp through services provided by the Harvard Clinical and Translational Science Center. Each sample volume will be approximately 3 teaspoons, for a total of 6 teaspoons drawn over the entire study.

All efforts will be made to protect subject privacy, and samples will be labeled with codenames and medical record numbers. The sponsor will not have access to information that identifies participants' samples. Results from laboratory testing (i.e. laboratory values) may become a part of the subjects' MGH medical records, however no information regarding participation in the study will become a part of the medical record.

Subject Visits:

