Cambridge Neuropsychological Test Automated Battery (CANTAB) (at screening or baseline, week 6 and week 12): CANTAB is a computer-based system designed to look at frontal lobe (executive functioning). Select subtests will include the following:

- Spatial Working Memory (SWM), tests comprehension, learning and reversal.
- Stockings of Cambridge (SOC), assesses spatial planning and motor control.
- Intra-Extra Dimensional Set Shifting (IED), tests rule acquisition and attentional set shifting.
- Reaction Time (RTI), measures speed of response.
- Rapid Visual Information Processing (RVP), tests sustained visual attention.
- Affective Go/No-go (AGN) assesses information-processing biases for positive and negative stimuli.
- Verbal Recognition Memory (VRM), assesses immediate free recall, and immediate and delayed recognition memory
- Cambridge Gambling task (CGT), to assess decision-making and risk-taking behavior.

Clinician rated assessments (rated at each in-office study visit, unless otherwise noted):

- Global Assessment of Functioning (GAF) scale. The GAF will assess global functioning using a scale from 1 (worst) to 100 (best). This will be collected at all study visits, excluding the screening visit.
- Clinical Global Impressions (CGI) scale for ADHD. The CGI is a measure of illness severity, improvement, and efficacy of treatment.
- Adult ADHD Investigator Symptom Rating Scale (AISRS). Each of the individual symptoms of ADHD is rated 0 to 3 on a scale of severity.
- Adverse Experiences (collected at all visits excluding the screening and baseline visits) and Concomitant Medications.

Subject rated scales (all scales rated at baseline, week 6, and week 12 or drop visit, unless otherwise noted):

- The 18-item ADHD Self Report Rating Scale (ASRS) to evaluate frequency of ADHD symptoms on a scale of 0 to 4.
- The 86-item Behavior Rating Inventory of Executive Function Adult Form (BRIEF-A) to assess levels of executive function deficits. ³⁶ This will be collected at baseline and at Week 12.
- The Adult Self-Report Form (ASR) to measure a wide range of psychiatric syndromes (i.e., depressive problems, anxiety problems, antisocial personality problems) in adults. The ASR provides dimensional scale scores for each syndrome that are age- and gender-normed. ³⁷
- The 16-itm Quality of Life Enjoyment & Satisfaction Questionnaire (Q-LES-Q) to measure overall satisfaction across different aspects of daily life. ³⁸

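### Relating baseline BRIEF deficit to BRIEF improvement puts the same baseline score on both sides, so the described association is pushed upward even with no effect (minor)

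*Combined protocol and SAP*

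**What the plan says.** The predictor analysis appears twice.

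- **Section VI, Biostatistical Analysis.** The sentence opens "We will also explore descriptively whether baseline erythrocyte magnesium level" and goes on to ask whether "deficits in BRIEF or CANTAB ratings as measured against norms predict improvement on AISRS or BRIEF ratings". Three predictors and two outcomes give six pairs, and BRIEF on BRIEF is one of them.
- **Section II, Specific Aims.** The aim is to see whether "deficits on BRIEF or neuropsychological tests predict improvements on AISRS or BRIEF measures". BRIEF on BRIEF is not excluded here either.

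On timing, Section V (Assessments and Instruments) says of the BRIEF-A: "This will be collected at baseline and at Week 12". The Visual Timeline agrees and labels the last column as week 12 or drop. Under Safety Assessments, subjects who leave early are "asked to complete all tasks scheduled to take place on the final study visit at the time of study discontinuation". So there is one score before treatment and at most one after it.

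On change, Section VI says of AISRS, BRIEF and CANTAB that "we will compare pre-treatment and study visit values of measures using paired t-tests". It describes the study as single-arm and open, with 15 subjects receiving the agent. No repeat baseline, adjustment or caveat is given for the predictor analysis.

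**The concern.** Improvement is the baseline score minus the later score. A subject whose baseline BRIEF happens to be recorded too high looks more impaired, and then appears to improve more when the score returns to its usual level. Expressing the deficit against norms rescales the baseline score but leaves its error in place.

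With one arm, nothing in the data shows what association would arise without the agent. A reader shown a moderate positive correlation would naturally conclude that more impaired adults benefit more. Section I says the pilot is meant to "guide development of future more definitive doubleblind study of the selected outcomes", so such a pattern could be carried forward.

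**Working it through.** The documents give no figure for this analysis, so there is none to reproduce.

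**Inputs**
- From the documents: n = 15, one arm, one baseline BRIEF-A score, one week 12 or drop score.
- Assumed, because the documents do not give them: retest correlation r from 0.6 to 0.9; k = week 12 SD / baseline SD, from 0.9 to 1.25; bivariate normal scores.

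**Formula.** Let X be the baseline score and Y the week 12 score, scored so that higher means more deficit, with improvement X - Y. Then

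corr(X, X - Y) = (1 - rk) / sqrt(1 + k² - 2rk),

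which is sqrt((1 - r)/2) when k = 1. The slope of improvement on baseline, in baseline SD units, is 1 - rk. A uniform shift in every subject's score changes neither quantity.

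**Equal spread (k = 1), no effect.** For example, r = 0.7 gives sqrt(0.30/2) = sqrt(0.15) = 0.39. The last two columns come from 100,000 simulated samples of 15.

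| r | Expected correlation | Extra apparent gain per 1 SD worse at baseline | Samples with positive correlation | Middle 95% of sample correlations |
|---|---|---|---|---|
| 0.6 | 0.45 | 0.40 SD | 96% | -0.07 to 0.79 |
| 0.7 | 0.39 | 0.30 SD | 93% | -0.14 to 0.76 |
| 0.8 | 0.32 | 0.20 SD | 88% | -0.22 to 0.72 |
| 0.9 | 0.22 | 0.10 SD | 80% | -0.32 to 0.67 |

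For scale, Hypothesis 2c counts executive dysfunction as reduced when it is "defined by a 0.5 standard deviation improvement on BRIEF-A self-report total or subscale scores". Section VI does not say which SD.

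**Unequal spread.** Expected correlation:

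| k | r = 0.6 | r = 0.7 | r = 0.8 | r = 0.9 |
|---|---|---|---|---|
| 0.9 | 0.54 | 0.50 | 0.46 | 0.44 |
| 1.1 | 0.36 | 0.28 | 0.18 | 0.02 |
| 1.25 | 0.24 | 0.14 | 0.00 | -0.22 |

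The sign turns where rk = 1, for example at k = 1/0.8 = 1.25 when r = 0.8. A k other than 1 may itself reflect real change.

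**The push is still there when the sign turns.** Let rel be the reliability of the baseline score and b the slope of true improvement on true baseline. The observed slope is rel × b + (1 - rel). An observed slope of 0 therefore means b = -(1 - rel)/rel. At rel = 0.8 that is -0.2/0.8 = -0.25: the more impaired subjects truly gain less, and the observed data show no relation.

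**Missed drop visits.** If a subject has no later BRIEF-A score and the baseline is carried forward, the change is 0. With an assumed 3 of 15 such subjects and k = 1, the mean sample correlation at r = 0.7 falls from 0.37 to 0.33, so the artefact remains.

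**The case against.** The strongest reply is that nothing in the plan is false. It promises only to describe an association, and baseline severity does predict observed change whenever rk is below 1. The error arises only if someone reads the association as a differential benefit, and no section says that. The study is declared open, single-arm and exploratory, so no pre-post result in it separates effect from regression to the mean. This limits the weight of the point but does not remove it. Descriptive output is read by its sign and size, and no section warns about this pair.

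Two qualifications stand. Section VI speaks of BRIEF-A total or subscale scores, so deficit on one subscale could be set against change on another; overlap would then be partial or confined to correlated error. And a positive association is the no-effect expectation only with similar spread, as the second table shows.

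A reader might infer more than the documents support:

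- **Inflated false-positive rate.** The 0.05 alpha follows the sentence on paired t-tests, and the predictor analysis is called descriptive with no test named.
- **A plan to choose a subgroup.** Section I mentions selected outcomes, not selected subjects. Subgroup choice is a risk, not a stated intention.
- **All six pairs are faulty.** Only BRIEF on BRIEF shares a score. BRIEF on AISRS could carry a smaller bias if errors at the same visit are correlated, but that is speculative. With an assumed error correlation of 0.3 and BRIEF reliability of 0.8, it would be 0.3 × sqrt(0.2/2) = 0.09.

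**Conclusion.** The concern holds, as a minor point about one descriptive pair. When the same or overlapping BRIEF scores are used on both sides, the planned association is biased upward, and neither the norms nor the design corrects it. With no effect and similar spread, the expected correlation is about 0.45 to 0.22 over r = 0.6 to 0.9; a larger week 12 spread can bring it to zero or below.

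The mechanism is certain under that overlap. Its size is not, because r and k are assumptions. Hypotheses 1 to 3 do not depend on this analysis.

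**What to change.** **Preferred: remove the one pair.** Each section keeps its own scope, because Section II refers to neuropsychological tests generally and Section VI to CANTAB.

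- Section VI: *Baseline erythrocyte magnesium and CANTAB deficits will each be examined descriptively against improvement in AISRS and in BRIEF; baseline BRIEF deficits will be examined against improvement in AISRS only.*
- Section II: *We will explore red blood cell magnesium at baseline, and deficits on the neuropsychological tests, as predictors of improvement in AISRS and in BRIEF; baseline BRIEF deficits will be explored as predictors of improvement in AISRS only.*

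**If the pair is kept**, add to both sections: *Where baseline BRIEF is both the predictor and the start of BRIEF change, shared measurement error pushes the association upward, and with similar spread at baseline and week 12 a positive association is expected with no effect. We will report both SDs and the correlation between the two scores. We will not take this association as evidence that more impaired subjects benefit more, or use it to choose a subgroup for a later study.*

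Two apparent repairs are not recommended:

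- **Subtracting the no-effect value.** At n = 15 an observed r of 0.8 has a 95% Fisher interval of 0.49 to 0.93, which puts the equal-spread no-effect correlation anywhere from 0.51 to 0.19.
- **Relating change to the mean of the two scores.** This gives a mean correlation of 0.00 with no effect and equal spread. But the covariance of X - Y with X + Y is var(X) - var(Y), so it compares spreads and does not predict from baseline.

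The cost is a sentence or a short statement in two places and no new data. The downside is that one exploratory association is lost or its use is limited.
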